- g. Postural sway (three conditions) The postural sway test is a measure of a person's ability to maintain balance while standing still. It involves measuring the amount of sway or movement that occurs in a person's body while they are standing in a stationary position. This test is commonly used in clinical settings to assess balance and gait disorders, as well as in research studies to investigate the effects of various interventions on balance. We will conduct the test in three conditions: 1) distance between foot is as wide as the shoulder, 2) distance between feet is twice as wide as the shoulder, and 3) distance between foot is as wide as the shoulder and the knee is bent to lower the center of gravity. Condition 1 is also tested first and Condition 2 and 3 are conducted in random sequence.
 - i. the participant is standing on the treadmill (as shown in Fig. 9) with a protection harness connecting the rail.

[figure not shown]

Fig. 9: The split treadmill, which is used in the protocol.

- ii. the physical therapist instructs the participant to get into one of the conditions and keep the arm on the side of the body
- iii. the participant are instructed to sway as far forward and far backward as possible without taking a step either forward or backward
- iv. a metronome is set at 0.25hz and the participant is instructed to finish one swing cycle in each beep
- v. the participant will have 5-10 second to try to get a comfortable sway range
- vi. After the verbal confirmation from the participant (“I am ready to start”), the sway efforts will last about 1-3 minutes to finish 60 sway cycles.
- vii. After each condition, the participant will be offered 2 minute break before the next one starts.
- h. Timed Up and Go (TUG) Tests with/out secondary tasks are a clinical assessment used to determine a patient’s risk of falling. The TUG alone will be conducted first and the TUG with secondary tasks will be followed. Each test will be conducted three times with 2 min breaks between the TUG alone and TUG with secondary tasks. An illustration of this task can be seen in Fig 10.

[figure not shown]
A

Fig. 10: setup of a TUG task. 1: on command, the subject rises from the armchair; 2: the subject walks 3 meters; 3: the subject turns around; 4: the subjects walks back to the chair; 5: the subjects sits back on the chair.

- i. A researcher will position a chair in an open space leaving at least 4 meters in front of the chair for the participant to walk.

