- ii. The researcher will mark off a space 3 meters in front of the chair.
- iii. The participant will start seated in the chair provided by the researcher.
- iv. At the researcher's instruction, the participant will stand up from the chair, walk to the marked spot 3 meters in front of them, turn around, walk back to the chair, and sit down.
- v. The researcher will start a time when they instruct the participant to stand, and end the timer when they sit back down.
- vi. (optional) Secondary tasks are often incorporated into TUG tests to increase utility of the test in identifying fall risks. We will be using an auditory stroop task to evaluate the cognitive load of the participant.
 1. While performing the TUG task, a speaker will sound a 500ms sound clip of the word "High" or "Low" in either a high pitch (360Hz) or a low pitch (180Hz), although these frequencies may be adjusted based on individual needs to ensure there is a clear distinction.

2. After each word is played, the participant will be asked to verbally respond with "High" or "Low" based on the pitch of the sound, but not the word spoken.
3. The speaker will produce new sound clips in random intervals of 2-3 seconds, the participant will respond after each sound clip. The number of sound clips and the number of correct responses are recorded for later analysis.

- i. Anticipated disturbance
 - i. The participant will stand on the treadmill with feet shoulder width apart, one foot on each belt, facing the perturbation platform as illustrated in Fig. 11.
 1. The platform delivers perturbations through a hanging weight which is a soft weight ball selected to be approximately 10% of the participant's body weight (BW) (± 5 lbs).
 2. The platform will be bolted to a rail, which is used for the patent protection, on the top of the treadmill.
 3. The weight is connected to a set of handlebars by 2 cords via a series of pulleys. An electromagnet is used in series with one of the cords to control the connection of the handlebars to the weight.
 4. When the electromagnet releases, the weight drops and causes the handlebars to either be pulled away from the participant or pushed towards them.
 5. An LED light at eye level with the participant will turn on exactly 1 second before the weight drops.
 6. The LED light will turn off exactly before the weight drops.
 7. Two different conditions will be tested:
 - a. Condition 1: 10% BW Push, the handlebars will be pushed towards the participant.

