5. Seven – eleventh visits: These visits are designed to give participants needed training, so participants are able to integrate the action of the powered prosthetic ankle with their full body motion for various tasks. To ensure that contribution of the training procedure to the performance changes are considered, all the participants will go through the training with the prostheses aligned with their group.

- a. EMG mounting (optional for patients use the powered prosthesis)
 - i. This is done following the procedure mentioned in visit 2, steps b.ii - b.vii.
- b. Protection harness mounting
 - i. This is done following the procedure mentioned in visits 3-4, step 3.
- c. Transition between sit and standing
 - i. The participant will start the task seated in a chair.
 - ii. The participant will be asked to lean forwards and stand up from the chair, using the armrests for support if needed.
 - iii. The participant will remain in the standing position, standing up right with back straight, for a few seconds.
 - iv. The participant will be asked to then transition from standing back to sitting in the chair.
 - v. This process will repeat for up to twenty trials. The participant will be offered the chance to rest for 2-3 minutes after 10 trials finished.

[figure not shown]

Fig 16: setup of the transition between sit and standing

- d. Single limb balance
 - i. While wearing the safety harness, the participant will begin by standing on the treadmill with feet shoulder width apart, with one foot on each of the treadmill belts.
 - 1. Handrails will be positioned on either side of the treadmill to use for support as shown in Fig. 9.
 - ii. Participant will be asked to raise their non-prosthetic foot off the ground and to balance on their prosthetic side as long as they are comfortably able to do so.
 - iii. The trial will end either when the participant's non-prosthetic foot touches the ground, or when the participant needs to use a handrail for support.
 - iv. Between trials a stool will be provided to allow the participant to sit and rest until they are ready to resume.
 - v. The trial will repeat 10 times..
- e. Squats
 - i. The participant will stand on the treadmill with feet shoulder width apart, toes facing forward, and one foot on each belt of the treadmill.
 - ii. The participant will be asked to raise their arms out in front of them and slowly bend their knees and lower their body towards the ground while keeping their back straight and chest lifted

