 - 1. If the participant feels unstable or unbalanced at any point they may use the handrails on either side of the treadmill to support themselves.
 - iii. The participant will bring their body as low to the ground as they are comfortable doing while maintaining balance, ideally until their thighs are parallel to the ground.
 - iv. The participant will try to hold at the lowest position for 3 seconds if possible.

- v. The participant will straighten their knees to stand back up and return to the starting position.
- vi. Squats will be done in sets of 3, with up to 5 sets done over the course of the visit.
- vii. a 2 minute rest will be given after each set
- f. Arm raise and reaching
 - i. Participant will stand with feet shoulder width apart and both feet pointing forwards
 - ii. Participant will raise their dominant arm to a 90 degree angle in front of them while making a fist with their hand
 - iii. Participant will be instructed to "Reach as far as you can forward without taking a step"
 - iv. After doing so and holding their position for a few seconds, the participant will be instructed to lower their arm and return to the standing position.
 - v. The task will be repeated up to 10 times.
- g. Postural sway
 - i. This is done following the procedure mentioned in visits 3-4, step g.
- h. Weight transfer
 - i. Participants stand with feet shoulder-width apart and place equal weight on both feet.
 - ii. Slowly shift the weight onto the prosthetic foot while keeping the knee slightly bent and the other foot flat on the ground.
 - iii. Hold this position for three seconds and then shift the weight back onto both feet.
 - iv. Repeat the process with holding time increases to 5 seconds or the participants find it difficult to increase the holding time.
 - v. Conducting three more repetitions.
- i. Rocker board on either limb
 - i. The participants begin by standing on the rocker board, which is put on the treadmill, with their feet shoulder-width apart and parallel to each other. Hold onto the rails if necessary, for balance.
 - ii. Shift the weight onto the prosthetic foot and allow the board to rock forward. Keep the knee slightly bent to absorb the movement and maintain balance.
 - iii. Hold the forward position for 3-5 seconds and then rock back onto both feet.
 - iv. As you become more comfortable with the movement, try increasing the range of motion and speed of the rocker board.

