 - vi. There will be up to 10 trials over the course of the visit, with 2 minutes of rest between each trial.
- l. Arise from chair is part of the Amputee Mobility Predictor (AMP) Assessment and is used alongside a series of other mobility tasks to quantify the overall mobility of an amputee.
 - i. Participant is instructed to sit in a chair with the seat at a height between 40-50cm.
 - ii. Participant is instructed to cross arms over chest.
 - iii. Participant is instructed to stand up. Their performance is scored from 0-2 as follows:
 - 1. Unable to stand without assistance (score = 0)
 - 2. Able to stand but requiring multiple attempts (score = 1)
 - 3. Able to rise in a single attempt (score = 2)
- m. Standing Reach Task is part of the AMP Assessment and is a clinical evaluation for determining the range of a participant's dynamic balance.
 - i. Participant will stand on the treadmill while wearing the safety harness, keeping feet shoulder width apart and one foot on each belt of the treadmill.
 - ii. Participant will wear safety harness and have arm rails available for support.
 - iii. The participant will be instructed to raise their dominant arm 90 degrees in front of them while continuing to stand straight.

- iv. A researcher will stand off of the treadmill in front of the participant and hold a ruler 12 inches from the participant's extended hand. The ruler will be aligned midline to the sternum.
- v. The participant will be instructed to lean forward and grasp the ruler.
- vi. the participant's performance will be evaluated on a score of 0-2 as follows:
 - 1. Unable to grasp ruler (score = 0)
 - 2. Able, but requires use of arms for support (score = 1)
 - 3. Able without arm support (score = 2)
- n. EMG electrodes remove
 - i. This is done following the procedure mentioned in visit 2, step c.
- o. Protection harness remove
 - i. This is done following the procedure mentioned in visit 3-4, step o.
- p. Discuss the participants about their expectation of the next visit
 - i. A researcher will describe what will be done in the next visit and ask the participants to inform the research team if any issues are noticed.

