- 6. Twelfth-thirteenth visit (duplicate of Third and fourth visit). These visits are used to evaluate the impact of the training program on the performance of the participants to conduct tasks which are not included in the training procedure. Each participant will conduct the task with both passive and powered prosthetic legs on different days.
- 7. Fourteenth-fifteenth visits (duplicate of Third and fourth visit). These visits are used to understand the long term effects of the training program on the participants. These visits will be conducted three months after the 13th visits.

Devices Used in the Research:

- Powered ankle prosthesis
 - This is a custom built minimal risk device shown in Fig. 1.
 - The device is designed so that no moving parts are directly attached to the user's prosthetic socket.
 - This minimizes risk of personal injury and damage to the socket
 - The procedure for putting on this device is described in the second visit, step a.
 - Safety precautions, such as the fall prevention suit and handrails used throughout the study, will ensure the risk of falls while using the device is minimal.
- Disturbance system
 - This is a custom built minimal risk device illustrated in Fig. 11.
 - The system is securely attached to the ceiling minimizing risk of it falling and causing damage
 - The weight used to generate the disturbance will never exceed 10% of the participant's body weight, minimizing risk that the disturbance will cause the participant to fall or stumble.
 - A light will flash before the disturbance occurs, ensuring the participant isn't caught off guard by the disturbance and can brace accordingly.
- Fall prevention suit
 - This device is off the shelf by not a medical device
 - This device is used on label and as approved

- This device is being used simply as a tool for fall prevention.
 - The procedure to put on this device is shown in Fig. 5.
- Instrumented treadmill (Registered Establishment Number: 1530895)
 - The device is off the shelf
 - The device is used on label and as approved
 - The device is being used simply as a tool for data collection in the research
 - The device is fixed on the ground and the participants will step on it after the treadmill is powered up. The participants will step off before the treadmill is powered off.
- VICON motion capture system (Registered Establishment Number: [1000377231](#))
 - The device is off the shelf
 - The device is used on label and as approved

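### Visits 12–13 are described as testing untrained tasks, but postural sway, one of their seven performance tests, is also a training step in visits 7–11

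*Protocol*

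**What the plan says.** Four places in the protocol's visit schedule bear on this point.

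- **Item 6 (Twelfth-thirteenth visit)** makes these visits a duplicate of the third and fourth. Their purpose is to "evaluate the impact of the training program on the performance of the participants to conduct tasks which are not included in the training procedure". It adds: "Each participant will conduct the task with both passive and powered prosthetic legs on different days".
- **Item 3 (Third and fourth visits), step g** is postural sway: "We will conduct the test in three conditions", which are defined by foot spacing and knee bend.
- **Item 5 (Seven – eleventh visits), step g** is also headed postural sway. Its whole content is a cross-reference: "This is done following the procedure mentioned in visits 3-4, step g".
- **Item 5, introduction**, says who is trained and on what: "all the participants will go through the training with the prostheses aligned with their group".

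Nothing in item 5 takes sway out of training, and nothing in item 6 takes it out of the repeated evaluation.

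**The concern.** Item 6 gives the only stated purpose of the evaluation that follows training, and so sets how its results will be read. A gain on an untrained task suggests that training has carried over to something new. A gain on a task practised in training may only show that the participant has become better at that test. For sway the second explanation cannot be excluded, because the training step and the test are the same procedure.

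The point is sharpest on the device each participant trained with, where sway has been rehearsed directly. On the other device a gain could show carry-over between devices, but still on a task that has been practised. In neither case is sway an untrained task, yet the sentence as written would let it be reported as one. What is at stake is the interpretation of the sway result, in a trial whose subject is postural control.

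**Working it through.** The protocol gives no figure to reproduce here. The check compares two lists.

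**Step 1. Tests at visits 12–13.** These are the performance tests of item 3, steps g to m, because item 6 duplicates that item. TUG with and without the secondary task counts as one test, the stance variants as three. The balance-confidence questionnaire (step q) is not a performance test and is left out.

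1. Postural sway (g)
2. TUG (h)
3. Anticipated disturbance (i)
4. Object pick-up (j)
5. Stance, eyes open, firm surface (k)
6. Stance, eyes closed, foam (l)
7. Stance, eyes closed, incline (m)

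Total: 7.

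**Step 2. Training steps.** Item 5, steps c to m, lists sit–stand transitions, single-limb balance, squats, arm raise and reaching, postural sway, weight transfer, rocker board, stool stepping, stop-and-go walking, arise from chair, and standing reach. Item 4 (visits 5–6) covers muscle coordination, control of the prosthetic or virtual ankle, and an ankle posture test. None of the item 4 tasks is among the seven.

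**Step 3. Match by named procedure.** Only postural sway is on both lists. The match needs no judgement about similarity, because the training step points to the test step by its letter. Tests repeated in training: 1 of 7. Tests not repeated as named procedures: 7 − 1 = 6.

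**Step 4. Amount of rehearsal.** The protocol lists the tasks for visits 7–11 together and does not expressly say that each task is run at each visit. If one assumes that sway is run at all five visits and nothing is skipped, a participant has 1 + 5 = 6 sway sessions on the trained device before visit 12 (one baseline, five training) and 1 on the other device. Clinicians may have visits or tasks skipped, so the possible range is 0 to 6 on the trained device and 0 to 1 on the other. The conclusion does not depend on this count. It needs only that sway is a scheduled training step.

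**The case against.** The strongest reply is that this is one loosely worded sentence. It describes six of the seven tests correctly and does not say that every test is untrained. The protocol ranks no outcomes and announces no transfer claim for sway, and labelling of outcomes is often left to an SAP, which is not shown here. Much of this stands as a limit on the size of the point. It does not remove the point: the protocol misdescribes its own schedule, and a separate analysis document would not correct that sentence.

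A second reply is that clinicians may recommend skipping tasks. That is decided participant by participant and leaves sway in the training schedule. It only makes the amount of rehearsal vary.

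A reader might also infer more than the documents support.

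- **That other tests are trained too**, because training includes squats (compare object pick-up), sit–stand work and stop-and-go walking (compare TUG), or rocker board, single-limb balance and weight transfer (compare the stance tests). These are related movements, not the same procedures. Training components and then testing a different composite task is an ordinary way to look for transfer, and it does not contradict item 6. Sorting the six tests by shared movement would be a matter of judgement.
- **That the group comparison is compromised.** It is not. Both groups go through the training, and training on the assigned device is part of what is being compared.
- **That visits 14–15 contain the same contradiction.** They repeat the same tests, but item 7 gives them a different purpose, long-term effects, without restricting it to untrained tasks.

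**Conclusion.** The concern holds in limited form. The purpose stated for visits 12–13 is wrong for 1 of the 7 performance tests. A sway result there on the trained device may reflect practice of the test itself, and sway cannot support a conclusion about transfer to untrained tasks. The other six tests fit the stated purpose in the sense that training does not repeat them as named procedures.

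This rests on reading the cross-reference in item 5, step g, at face value and on counting steps g to m of item 3 as seven tests. Trained-task outcome here means only that a measured test is also a training step. It implies no ranking of outcomes. The size of any rehearsal effect cannot be derived from the protocol and is not claimed.

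**What to change.** Reconcile item 5, step g, with item 6:

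1. Correct the purpose sentence of item 6, for example: *These visits assess the effect of training on postural sway, which is also practised in visits 7–11, and on six tests that training does not repeat as named procedures.*
2. Report sway at visits 12–13 as a trained-task outcome.
3. Rest any conclusion about untrained tasks on TUG, anticipated disturbance, object pick-up and the three stance tests.

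The cost is one sentence and one outcome label. No test, training step or visit changes. The downside is small: the untrained-task conclusion rests on six tests instead of seven.

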 - b. Condition 2: 10% BW Pull, the handlebars will be pulled away from the participant.
 - ii. A researcher will adjust the height of the perturbation platform to ensure the handle bars are at shoulder height for the participant.
 - iii. The participant will be instructed to reach out and hold onto the handlebars of the perturbation platform.
 - iv. The participant will be instructed to try and brace for the perturbation and try not to move their feet as the perturbation occurs, however if they lose balance or feel unstable they may take a step to steady themselves.
 - v. First, a round of practice trials will be held so the participant can be made aware of the strength of the perturbations that will occur.
 1. The participant will be informed on the direction of the perturbation with the handlebars either being pulled away or pushed towards them.
 2. The participant will complete each condition 3-10 times before evaluation.

3. For the repetition of each condition, the researcher will count down from 3 down to 1, timed so that they will say 1 just as the LED turns on.
4. For the other 2 repetitions of each condition the participant will rely solely on the LED to see when the disturbance will occur.

vi. For the evaluation portion of the task:

1. Each condition will be tested 10 times
2. For each of these trials the participant will rely on the LED to determine the timing of the weight drop.
3. In between conditions the participant will take a 2 minute break.

[figure not shown]

Fig. 11: **Experimental Platform Illustration.** Participant stands upright while holding a handlebar at arm's length and shoulder height. The handlebar is attached to a suspended weight by two cords. One cord is directly attached to the weight (solid) and the other is attached to the weight with an electromagnet in series, that, when switched off severs the cord's connection with the weight (Release Cord). In this illustration the perturbation platform delivers a pulling perturbation on the participant. The direction of the perturbation is switched by changing the location of the solid and release cord. a) LED light. The LED light is switched off 0.6s before the electromagnet is released providing the participants with a notification of the impending perturbation. b) Perturbation load. Weight is normalized to the participants body weight (10%). c) Pneumatic Artificial Prosthetic Ankle.

- j. Pick up objects from the floor

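### The ± 5 lbs load tolerance in the disturbance test does not secure the stated 10% body-weight ceiling, and the LED cue is described in two conflicting ways

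*Protocol*

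**What the plan says.** **Load.** Under Devices Used in the Research, Disturbance system, the Protocol states: "The weight used to generate the disturbance will never exceed 10% of the participant's body weight". It gives the purpose as "minimizing risk that the disturbance will cause the participant to fall or stumble". The operating instruction is in Third and fourth visits, step i (Anticipated disturbance), item i.1. There the ball is "selected to be approximately 10% of the participant's body weight (BW) (± 5 lbs". The two test conditions and the Fig. 11 legend refer to 10% of body weight and give no tolerance.

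**LED cue.** Item i.5 reads: "An LED light at eye level with the participant will turn on exactly 1 second before the weight drops". Item i.6 reads: "The LED light will turn off exactly before the weight drops". In practice (item v.3) the researcher's countdown is "timed so that they will say 1 just as the LED turns on". The Fig. 11 legend reads: "The LED light is switched off 0.6s before the electromagnet is released providing the participants with a notification of the impending perturbation". For the evaluation trials, item vi.2 states: "For each of these trials the participant will rely on the LED to determine the timing of the weight drop".

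**Where it recurs.** Visits 12-13 and 14-15 duplicate visits 3-4, so the task is scheduled at six visits.

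**The concern.** The load ceiling is worded as absolute and is offered as a reason why a custom-built device is of minimal risk. The operating instruction has a tolerance on both sides of the target, and no step tells staff to stay at or below it. Staff who follow item i.1 exactly can therefore exceed a limit that the same document says is never exceeded.

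The LED is what makes the disturbance anticipated. If the document gives two accounts of when the light goes off, and of whether light-on or light-off is the signal, then the stimulus that participants are told to rely on is not fixed. What is at stake is a stated device property that the procedure does not support, and an ambiguous definition of one evaluation task.

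**Working it through.** **Inputs.** Ceiling: 10% of body weight (Disturbance system). Selection rule: about 10% of body weight, ± 5 lb (item i.1). Largest eligible body weight: 300 lb (Inclusion/Exclusion). The Protocol gives no other body weight, so 200, 150 and 120 lb below are assumptions.

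**The Protocol's own figure.** At 300 lb the ceiling is 0.10 × 300 = 30 lb.

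**Upper permitted load.** With BW in lb, the share is (0.10 × BW + 5) / BW. The excess over the ceiling is 5 / BW, which is positive at any weight.

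| Body weight | Ceiling | Upper permitted load | Share of BW | Excess, percentage points |
|---|---|---|---|---|
| 300 lb (limit) | 30 lb | 35 lb | 35/300 = 11.7% | 1.7 |
| 200 lb (assumed) | 20 lb | 25 lb | 25/200 = 12.5% | 2.5 |
| 150 lb (assumed) | 15 lb | 20 lb | 20/150 = 13.3% | 3.3 |
| 120 lb (assumed) | 12 lb | 17 lb | 17/120 = 14.2% | 4.2 |

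The excess is 5 lb throughout and is largest, as a share of body weight, in the lightest participants.

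**Loads that satisfy both statements.** These run from 5 lb below target up to the target: 25 to 30 lb at 300 lb, and 10 to 15 lb at an assumed 150 lb. Compliance with both is possible, but item i.1 does not require it.

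**Alternative reading.** If the 5 lb applied to body weight rather than to the ball, the upper share would be 0.10 × (BW + 5) / BW. That is 30.5/300 = 10.2% at 300 lb and 15.5/150 = 10.3% at an assumed 150 lb. The ceiling is still not secured.

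**LED, side by side.**

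| | Steps (items i.5, i.6, v.3) | Fig. 11 legend |
|---|---|---|
| Light on | 1.0 s before the drop | not stated |
| Light off | just before the drop, read as about 0 s | 0.6 s before release |
| Event presented as the cue | light-on (countdown tied to it) | light-off |

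Light-on at 1.0 s is compatible with the legend. The switch-off times are not compatible: 0.6 − 0 = about 0.6 s apart. The light would be lit for about 1.0 s under the steps, and for 1.0 − 0.6 = 0.4 s if the legend's switch-off is combined with the steps' switch-on. The device section says only that a light flashes beforehand, which fits either account and settles nothing.

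**Exposure.** Six visits × two conditions × 10 evaluation trials = up to 120 evaluation releases per participant, plus practice. The Protocol allows clinicians to skip visits or tasks, so this is a maximum.

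**The case against.** The best defence is that the two load statements can be read together: the device section caps the load, and item i.1 gives a working tolerance around an approximate target. A ball at or below 10% satisfies both. That stands as far as it goes, and it rules out saying that the safety statement is false or that a breach must occur. But no step says that the cap truncates the tolerance.

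On the LED, the steps agree among themselves and the outlier is a figure legend. Item i.6 gives no interval, so about 0 s is a reading of its wording. Both points are fair. The legend still cannot be set aside, because the device section refers to Fig. 11 as the illustration of the system.

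Three stronger inferences are tempting, and the Protocol does not support them:

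- *Participants are left unprotected against falls.* The harness goes on at step e and comes off at step o; participants may step if unstable (item iv); practice trials acquaint them with the strength and direction of the disturbance (item v); and every version of the light warns before release. The fall-risk section relies on the harness, handrail and walker, not on the load ceiling or the light.
- *The powered-versus-passive comparison is biased or made noisy by a 10-lb load span.* That span uses item i.1 alone and ignores the ceiling; with the ceiling it is 5 lb. It also needs a participant to receive different balls at paired visits. The ball is tied to that person's body weight, the paired visits are described as generally identical, and nothing suggests a change.
- *Participants get 0.4 s less warning under the legend.* Subtracting 0.6 s from 1.0 s compares light-off with light-on, which are different events and can both occur in one trial. Nor does the Protocol say that staff set the light trial by trial, so different cueing by different staff is conjecture.

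**Conclusion.** Both inconsistencies hold. The procedure permits a load 5 lb above the stated ceiling at every eligible weight: 11.7% of body weight at the 300-lb limit, and 12.5% to 14.2% over an assumed range of 200 down to 120 lb. The ceiling is therefore not secured, although a breach is not forced. The LED descriptions conflict on the switch-off time, by about 0.6 s if item i.6 is read as immediate, and on which event is the cue. The conflict over the cue event does not depend on that reading.

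This is a minor to moderate internal inconsistency. It is worth correcting because a stated safety limit on a custom-built device can be exceeded by following the instructions, and because evaluation trials depend on the cue. The other protections are unaffected, and no bias or effect on the trial's conclusions is shown.

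**What to change.** Reconcile item i.1 of the anticipated disturbance task with the Disturbance system entry under Devices Used in the Research, so that both state the same load limit. Reconcile the LED cue event and its timing across items i.5, i.6 and v.3 and the Fig. 11 legend, so that one sequence is given. The investigators must supply the values; this review does not choose them.

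Optionally, record the ball weight used at each evaluation visit (3-4, 12-13 and 14-15), so that compliance with the reconciled limit can be checked.

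The cost is a few lines of protocol wording and, if the option is taken, one recorded field per evaluation visit.
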